Pain thresholds are defined as the minimum intensity which must reach a stimulus to become in painful, as perceived and reported by the own person. Pressure pain threshold will be calculated using a digital handheld algometer (Wager Force One Model) which puts progressively heavier pressure over the skin surface. Heat pain threshold is obtained with a computerized thermal stimulator which progressively enhances the temperature of the skin with a small contact metal plate. In both cases, pressure and temperature increases to a constant pre-fixed rate, until the participant press a button to indicate she/he starts to feel pain. Pressure pain threshold is measured in kPa, whereas heat pain threshold is established as the temperature in degrees Celsius.

Although the specific CPM and TSSP protocols are not completely defined yet, we count with a wide catalogue of usually used instruments and equipment to perform these tests (Fernandes et al., 2019; O'Brien et al., 2018)

Conditioned Pain Modulation requires of two different painful stimuli applied in heterotopic body areas; thus, the conditioning stimuli (CS), tonic in nature, reduces the pain sensations from the phasic test stimuli (TS). As CS, we will use the ischemic pain produced by pressure cuff and/or the cold pressor test, which means the participant have to immerse their non-dominant hand into cold water. Regarding TS, we opt for the same procedures as to calculate the pain thresholds (i.e., digital handheld algometer and thermal stimulator), given that we aim to compare these isolated thresholds with those obtained

while the CS is present. The difference between these two measures is established as the CPM index.

Tentatively, Temporal Summation of Second Pain (TSSP) will be evoked with the thermal stimulator. After establishing the parameters which corresponds to a medium pain level (5/10 NRS) for each participant, it will be applied ten repetitive pulses with that temperature over the skin, separated by two and a half seconds. Patients have to rate the pain intensity which produces the first, fifth and last stimuli. The difference in pain intensity between the first and last pulse is established as the TSSP index.

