(Adams & Turk, 2015; Keefe et al., 2004; Jensen et al., 2011). Thus, these factors must be taken into account when assessing the efficacy of tES intervention and we intend to account them as covariates in statistical analysis.

Changes observed in criteria variables between pre- and post-evaluation must be equal or higher than the 30%, in order to ensure their clinical significance. It means that the improvement observed in self-reported questionnaires and in sensory testing (except for EEG) have to achieve or surpass the 30% of the original outcome. The direction of these differences depends on the specific scale; for example, it is expected a reduction in the global MPI score after treatment, but also a rise in pain thresholds. In the case of EEG, the analysis pre-post treatment are only subjected to the statistical significance. However, changes in brain activity patterns attributed to the tES will be tried to relate with improvement in clinical features.

Although all explained measurements are considered as success criteria of treatment, we selected pain intensity as the primary end point, taken as the average obtained from daily numerical rating scale. In this sense, participants will be classified into responders when they report, at least, a 30% decrease in their pain intensity. The rest of the variables are taken as secondary end points and are also regarded as treatment-efficacy indexes, basically the pain thresholds, life quality, physical functioning, interference caused by pain, pain unpleasantness, sleep quality, depression/anxiety, fatigue, caregiver burden and CPM/TSSP responses.

Table 1: End points of the clinical trial and their respective evaluation instruments

End points		Assessment tools
Primary end point	Pain intensity	Numerical Rating Scale of eleven points (0-10 NRS). Average obtained from daily self-reports during the fifteen days before treatment and the fifteen days after treatment.
Secondary end points	Global severity of chronic pain syndrome	Global and subscales scores of Multidimensional Pain Inventory (MPI).
	Interference caused by pain in daily living	Subscale score of Multidimensional Pain Inventory (MPI). Numerical Rating Scale of eleven points (0-10 NRS). Average obtained from daily self-reports during the fifteen days before treatment and the fifteen days after treatment.

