	Pain thresholds	Pressure pain threshold using a digital handheld algometer, measured in kPa. Heat pain threshold using thermal stimulator, measured in degrees Celsius.
	Life quality	Short Form Health Survey SF-36
	Physical functioning	Daily recorded physical activity using actigraphy technology. Subscales scores of Multidimensional Pain Inventory (MPI)
	Sleep quality	Pittsburgh Sleep Quality Index (PSQI)

	Daily recorded sleep quality using actigraphy technology.
Pain unpleasantness	Numerical Rating Scale of eleven points (0-10 NRS). Average obtained from daily self-reports during the fifteen days before treatment and the fifteen days after treatment.
Mood and emotional functioning	Hospital Anxiety and Depression Scale (HADS) Numerical Rating Scale of eleven points (0-10 NRS) for assessing daily anxiety. Average obtained from daily self-reports during the fifteen days before treatment and the fifteen days after treatment.
Fatigue	Modified Fatigue Impact Scale (MFIS) Numerical Rating Scale of eleven points (0-10 NRS). Average obtained from daily self-reports during the fifteen days before treatment and the fifteen days after treatment.
Caregiver burden	Zarit Burden Interview (ZBI) applied to the identified reference person in charge of caring the patient
Endogenous pain inhibition response	Score obtained from Conditioned Pain Modulation (CPM) procedure
Endogenous pain facilitation response	Score obtained from Temporal Summation of Second Pain (TSSP) procedure

	Global satisfaction with treatment and self-perceived improvement	Ad-hoc designed questionnaire
--	---	--------------------------------------

7. Data analysis plan

First of all, we will perform reliability analysis on sensory measures, such as pain thresholds, CPM and TSSP magnitudes. The Intraclass Correlation Coefficient to establish the degree of association and agreement among the two scores obtained for each test.

After applying the pertinent filters to EEG records and once the descriptive analyses of the sample have been done, we will observe the correlation of the CPM/TSSP response and the EEG registry with the clinical features of the sample, taking into account just the pre-treatment evaluation. In order to reinforce the results, we may add *Linear regression analysis* to verify whether the dysfunctions in central modulatory mechanisms and brain processing of painful stimulus (CPM, TSSP, EEG) can act as predictors of the symptoms severity of chronic pain patients.

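### The 30%-of-baseline responder rule cannot work for heat pain threshold in degrees Celsius and works poorly for the CPM index (for TSSP the problem is weaker)

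*Combined protocol and SAP*

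**What the plan says.** Section 6.2 sets a clinical-significance rule for pre-to-post change. Improvement in questionnaires and "sensory testing (except for EEG) have to achieve or surpass the 30% of the original outcome". The direction depends on the scale; the example given is that "it is expected a reduction in the global MPI score after treatment, but also a rise in pain thresholds". Only one measure is let off: "In the case of EEG, the analysis pre-post treatment are only subjected to the statistical significance".

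Table 1 lists the pain thresholds, CPM and TSSP as secondary end points. For heat the entry is "Heat pain threshold using thermal stimulator, measured in degrees Celsius". CPM compares the threshold alone with the threshold during the conditioning stimulus: "The difference between these two measures is established as the CPM index". For TSSP, "The difference in pain intensity between the first and last pulse is established as the TSSP index". Section 6.2 also says "Although the specific CPM and TSSP protocols are not completely defined yet".

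Section 7 defines a treatment respondent by the 30% improvement and puts everyone who does not meet it among the non-respondents. It runs a chi-square between arms for each endpoint and reuses the categories in logistic regression. The same section also analyses the endpoints as continuous values by repeated-measures ANOVA, and uses improvement as the outcome of linear regressions.

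**The concern.** A percentage of baseline is meaningful only if the scale has a true zero and baselines lie well away from it. Pain NRS and pressure threshold in kPa have a true zero. Temperature in Celsius does not, and a difference score can lie at, near or below zero.

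For heat threshold, the responder table risks being empty or nearly so in every arm, and an empty table could be mistaken for evidence of no effect. For CPM, and less so for TSSP, percent change is undefined at a zero baseline and the hurdle is trivially small near zero. The text also does not settle whether a patient starting at or below zero can respond. If that is decided after unblinding, the choice could be driven by the data.

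**Working it through.** The plan gives no figure to reproduce here beyond the 30% cut-off: no baseline mean, SD or reliability for any of these tests. Every other input below is an assumption, except the total of 120 and the 40/40/20% allocation, which come from sections 4 and 3.

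**Heat threshold: unit dependence.** A baseline of 44 °C (assumed) has a hurdle of 0.3 × 44 = 13.2 °C. The same temperature is 111.2 °F, and 0.3 × 111.2 = 33.4 °F, which is a rise of 18.5 °C. One patient faces two hurdles depending on the unit. This part of the argument holds at any baseline.

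**Heat threshold: size of the hurdle.** 0.3 × 40 = 12.0 °C and 0.3 × 48 = 14.4 °C. With baselines distributed N(44, 2.5²), the chance that a patient responds is the upper normal tail of

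z = (13.2 − true rise) / √(SD of change² + 0.09 × 2.5²).

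- True rise 3 °C, SD of change 1.5 °C: z = 10.2/1.677 = 6.08, so the probability is 6 × 10⁻¹⁰.
- True rise 5 °C, SD of change 3 °C: z = 8.2/3.092 = 2.65, so the probability is 0.4%, and 120 × 0.004 ≈ 0.5 patients.

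**CPM and TSSP: what the text leaves open.** At a baseline of zero the percentage cannot be formed. Read instead as a hurdle, it is zero, so any gain passes. For a baseline at or below zero, two readings fit the text: (A) improvement of at least 30% of the absolute value of the baseline; (B) such a patient is a non-responder.

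**CPM and TSSP: how much it matters.** Simulation: true index N(μ, 1), so μ is the mean in between-patient SDs; independent measurement error of SD 0.65–1 before and after (ICC 0.70–0.50); one session per phase; arms of 48/48/24; a true gain of 0.8 SD in both active arms; a 3×2 chi-square at 0.05. Improvement is taken as a rise for CPM and a fall for TSSP. The share of baselines at or below zero is Φ(−μ/√(1+e²)), where e is the error SD.

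| Mean/SD | Baseline ≤ 0 | A and B disagree on p<0.05, CPM | Same, TSSP |
|---|---|---|---|
| 0.5–1 | 20–36% | 26–41% | 22–40% |
| 2 | 5–8% | 14–16% | 6–9% |
| 3 | 0.6–1.7% | 4–7% | 1–2% |

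Repeat runs moved these ends by about one percentage point. With no true effect, each reading taken alone rejected in about 5% of trials.

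**Cost of the percentage form itself.** Compared with a fixed cut-off having the same null responder rate, reading A loses about 4–17 points of power for CPM at mean/SD 0.5–2. For TSSP it loses none.

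**The case against.** The strongest reply concerns CPM and TSSP, and much of it stands.

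- A reader might infer that the rule is undefined for every index at or below zero. It is not: a percentage fails only at exactly zero.
- A reader might also infer that a CPM index falling from −1.0 to −1.3 counts as a response, because the ratio is +30%. Section 6.2 asks for improvement, and a loss of inhibition is not improvement.
- Excluding patients with a baseline at or below zero is likewise poorly supported, because section 7 places everyone who does not meet the criterion among the non-respondents. Only readings A and B are therefore compared above.
- The background text before section 2 says that about 70% of chronic pain patients have reduced inhibition relative to healthy controls. That does not show that their CPM index is near zero, so the low mean/SD rows are possible but not established.
- The same text expects larger TSSP in patients, and a patient with no summation has none to reduce. TSSP is therefore the weakest part. Section 6.2 sets its stimulus "After establishing the parameters which corresponds to a medium pain level (5/10 NRS) for each participant"; the objection that a one-point change would then be enough for an index of 1–3 holds only if ratings are whole numbers.
- Sensory testing may be repeated within each phase. If two sessions were averaged, which is not specified, an error SD of 0.65 would become 0.65/√2 = 0.46, and disagreement at mean/SD 2 would fall to about 7% for CPM and 2% for TSSP.

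On scope, section 7 speaks of a clinical variable when it defines a respondent, and elsewhere sets clinical variables apart from biomarkers. That might leave out CPM and TSSP, but section 6.2 and the per-endpoint chi-square point the other way. Heat threshold is not in the biomarker list, so it stays in under either view. None of these replies rescues the heat rule.

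**Conclusion.** The concern holds, at minor severity. For heat threshold, confidence is high: the hurdle depends on the unit, and under the assumed baselines the responder chi-square would have essentially no responders to compare. For CPM, confidence is moderate. The rule is unclear at or below zero and trivial just above it. How often this changes a result depends on a mean/SD ratio that the documents do not give. For TSSP, confidence is low: the same ambiguity exists, but its effect is small once the mean index is 2 SD or more.

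A reader might infer that the ambiguity inflates false positives or undermines the trial's efficacy conclusion. The documents do not support that. Either reading, fixed in advance, is valid. The primary pain-intensity rule, pressure threshold in kPa and the repeated-measures ANOVAs are unaffected. What is exposed is the set of secondary responder chi-squares for these measures and the logistic regressions that reuse them.

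**What to change.** - In section 6.2, extend the exemption from EEG alone to EEG, heat pain threshold and CPM.
- In section 7, state that heat threshold and CPM are judged on absolute change, with the repeated-measures ANOVA and linear regression already planned, and that no treatment-responder chi-square or logistic regression takes them as outcome.
- For TSSP, either exempt it in the same way for consistency, or keep the 30% rule and state before unblinding that a baseline index at or below zero counts as non-responder.
- State how a zero baseline is handled for any other endpoint that can reach zero, such as the daily anxiety NRS, which has no minimum at entry.

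The pre-treatment split into CPM and TSSP respondents, and the use of both as predictors, can stay as they are. The cost is a few words in section 6.2 and a few sentences in section 7, with no new data or visits. The downside is that the exempted measures will have no responder rate on the common 30% scale.

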For planning the sample size for this research, we used Gpower (v.3.1.9.2) software. Sample size was estimated for repeated measures ANOVA with three groups (tDCS, tACS, Sham) and two measurements (pre-treatment vs. post-treatment). Statistical power (SP) was predetermined a priori with a value of SP=0.99 ($\alpha=0,01$) to increase the validity of the subsequent analysis and ensure that we do not miss any statistically significant result.

We based the calculation on the data extracted from the meta-analysis by Zortea et al. (2019), who reported a moderate effect size for reduction of pain levels ($F=0.68$) in chronic non-cancer pain patients using the tDCS montage stimulating M1. These results were obtained after comparing 380 patients receiving active tDCS versus 381 who were given Sham stimulation.

Assuming this moderate effect size and the rest of described parameters (SP=0,99), a total of 21 patients would be large enough to detect statistically significant changes in the whole sample. However, it cannot be ignored the non-despicable drop-out rates of this patient profile, corroborated by the own researchers in previous investigations. Besides, we are interested in assessing the effect size of the tDCS intervention among the different categories or types of chronic pain, just as defined by the ICD-11 (Treede et al., 2015), and that requires to create big enough comparable groups. For these reasons, we decided to recruit a larger number of participants, thus stablishing the sample size in 120 patients with refractory chronic pain.

Concerning this research, pain is defined as refractory, regardless of etiology, when it meets the two following conditions. First, multiple evidence-based biomedical therapies

used in a clinically appropriate and acceptable fashion have failed to reach treatment goals that may include adequate pain reduction and/or improvement in daily functioning or have resulted in intolerable adverse effects. Second, pain persists even after psychiatric disorders and psychosocial factors that could be influencing treatment outcomes have been assessed and appropriately addressed.

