Identified caregivers are invited to a brief face-to-face interview to evaluate their burden and health status. Given the exploratory character of this purpose, we do not set a priori sample size for caregivers, although the question about the caregiver will be formulated to all the patients.

5. Description of the treatment

Home-based transcranial electrical stimulation device consists of a custom headgear with fixed electrode sites and built-in cabling made for a simplistic setup for tDCS/tACS stimulation. Systems are equipped with strict dose control feature that provide reliable control over the intensity and timing of stimulation, turning these devices into a feasible and safe clinical alternative.

The equipment is specifically designed for easy and simplistic self-setup and allows the researchers to remotely check the position of electrodes and also monitor the stimulation session. This is possible because the devices have an Internet wireless connection and send the data obtained to an online platform, only accessible to the principal researchers.

From pre-stimulation set-up, to during stimulation monitoring, to post-stimulation confirmation, the device provides an intuitive and clear indication of electrode contact quality, facilitating the proper adjustments to ensure a successful stimulation. In case stimulation is aborted or interrupted, impedance is abnormal, or other faults are detected, the system will automatically abort or alter stimulation and the incident details stored. This system also allows researchers to supervise the treatment compliance.

¹ It must not be overlooked that patients with chronic pain can find difficulties/limitations to accomplish the basic daily tasks and thereby be partially dependant (Meulders, 2019; Zale et al., 2013)

Besides, these devices use a software which allows a double-blinded procedure. Neither the researchers nor the participants will know what kind of stimulation is receiving each of them.

The intervention plan comprises fifteen stimulation sessions applied with a daily frequency during an uninterrupted period of time which covers just over two weeks. Thus, sessions will be scheduled for each patient before the beginning of the treatment, arranging with the patient the hour frame for stimulation. Stimulation parameters/sites for each condition will be as follows:

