Besides, we will conduct simple ANOVA analyses to compare these indexes of pain processing and modulation (CPM, TSSP, EEG) between specific groups of patients, divided by type/origin of chronic pain and sex. We reserve the possibility of making *Cluster analyses* in the basis of the mentioned central biomarkers, following by an ANOVA comparison of clinical features between the emerged groups.

Besides, participants will be classified into CPM and TSSP respondents or non-respondents taking into account their results in these sensory tests. Those patients who report a significant increment in pain thresholds will be considered respondents; whereas the opposite applies for TSSP, as it must be detected a significant increase in perceived pain intensity in the last pulse compared to the first one. Depending on the proportions observed, it could be useful to divide TSSP respondents based on the degree of the pain sensitization. Regarding this sample division, we can compare the clinical profile of respondents and non-respondents patients using *Chi square statistic*.

As far as intervention efficacy is concerned, qualitative analyses will focus on differentiating the patients who effectively respond to treatment (Treatment-respondents) from those who do not improve (Non-treatment-respondent). Respondents are those

participants whose improvement in a certain clinical variable are equal or higher than the 30%; whereas non-respondents are all those who do not comply with this criterion. This variation is extracted from the comparison of pre- and post-treatment measurements.

Therefore, for each of the endpoints, we will obtain a number/percentage of respondents and non-respondents. Using the *Chi-square test*, we will compare the proportion of respondents between treatment groups to identify the most efficacious stimulation procedure. A separated analysis will be done for each described endpoint, which define what a respondent is.

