The main quantitative statistical analyses to assess the efficacy of transcranial electrical stimulation techniques consist of ANOVA-tests of repeated measures with three groups. Time-measures for each of the above-mentioned endpoints are taken as intragroup variables (pre vs. post), whereas intergroup measures refer to the received stimulation or treatment (tDCS vs. tACS vs. Sham). Thus, both clinical variables (for example, pain intensity, fatigue, sleep quality, disease severity and interference) and potential biomarkers (including brain oscillatory activity registered by EEG, CPM and TSSP response) are considered as intragroup variables.

Those covariates which show a significant correlation with clinical outcomes will be also included in their correspondent ANOVA analysis. These potential covariates are basically age, self-perceived stress, social support, catastrophism and medication intake.

All these statistical analyses will be repeated in separated groups of patients, created in the basis of sex, type and duration of chronic pain, among other characteristics. The objective is to assess whether the clinical outcomes depend on sex or diagnosis, as each tES could be more effective for specific diseases.

CPM/TSSP response and EEG pattern observed before the tES application are also regarded as potential predictors of the treatment efficacy. Thus, the pre-treatment indexes of these biomarkers will be used as independent variables in *Linear regression models*, which includes the clinical improvement in each endpoint as dependent measure. The procedure will be repeated with *Logistic regression analysis* establishing the respondent vs. no-respondent categories as dichotomic variable.

For last, we will register and assess the percentage of dropouts with their respective motives, in order to obtain an index of the feasibility of home-based tES approach. Client

satisfaction index and caregiver interview will also include questions about the capability of participants to manage with tES devices, data which will be qualitatively analysed.

8. Chronogram

WORKING PLAN (WP)		3	6	9	12	15	18	21	24	27	30	33	36
TASK	\ MONTH												
WP1. Development and selection of assessment and monitoring tools for refractory chronic pain patients													
Task 1.1.	Review of the literature and identification of the most common and important variables used as outcomes in clinical trials with chronic pain population.												

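### One primary endpoint is named, but all 14 endpoints count as success criteria, with no multiplicity control and no deciding test for the primary

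*Combined protocol and SAP*

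**What the plan says.** Section 6.2 (Evaluation methods and assessment tools) opens the key sentence with a concession, that "all explained measurements are considered as success criteria of treatment", and then selects pain intensity, averaged from the daily 0-10 rating, as primary. It goes on to call the remaining variables secondary but also indices of treatment efficacy. Table 1 has 14 rows: one primary and 13 secondary. Several rows carry more than one instrument.

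Section 7 (Data analysis plan) sets out two tests for each endpoint:

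- A chi-square comparing the proportion of 30% responders between the three groups: "A separated analysis will be done for each described endpoint, which define what a respondent is".
- A repeated-measures ANOVA with three groups and two times (before and after treatment), described as the main quantitative efficacy analysis.

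Section 7 then adds: "All these statistical analyses will be repeated in separated groups of patients", formed by sex, type and duration of pain and other characteristics. The number of strata is not given.

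Section 4 (Sample and recruitment) treats the caregiver aim differently: "Given the exploratory character of this purpose, we do not set a priori sample size for caregivers". Caregiver burden is nevertheless one of the 13 secondary rows.

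The only significance level is the 0.01 used for sizing in section 4; section 7 states none. The documents contain no multiplicity adjustment, no order of testing, and no statement that secondary or subgroup results are exploratory.

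**The concern.** A primary endpoint limits false positives only if the efficacy conclusion is tied to it. Here it is not. The plan gives the secondary endpoints standing as efficacy evidence, tests most of them twice, and invites claims within subgroups. An analyst following the text could report a significant result on fatigue, sleep or heat threshold as evidence that stimulation works, whatever happened to pain intensity.

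The primary has a gap of its own. Section 6.2 defines responders on it, and section 7 provides both an ANOVA and a chi-square, without saying which decides. An omnibus three-group test also does not say which contrast answers the hypothesis in section 2 that stimulation beats sham.

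**Working it through.** **1. The plan's own figure, to establish alpha.** Section 4 gives f = 0.68, alpha 0.01, power 0.99, three groups, two measurements and N = 21. The correlation between measurements is not stated; 0.5 is assumed, the default of the software used. For the group-by-time interaction:

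- noncentrality = f² × N × m / (1 − rho) = 0.4624 × 21 × 2 / 0.5 = 38.8, with 2 and 18 degrees of freedom;
- power = 0.994; the smallest N reaching 0.99 is 20, which becomes 21 for three equal groups.

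At alpha 0.05 the same calculation gives 18. So 21 is reproduced, and 0.01 was the level used.

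**2. Number of tests.** Satisfaction and self-perceived improvement are asked only at post-evaluation (section 6.1), so neither a pre-post ANOVA nor a 30% change can be formed for that row. That leaves 13 endpoints × 2 tests = 26 in the whole sample.

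**3. Arithmetic bound.** For k independent tests with no effect, the chance of at least one significant result is 1 − (1 − alpha)^k:

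- alpha 0.01: 1 − 0.99^13 = 12.3%; 1 − 0.99^26 = 23.0%
- alpha 0.05: 1 − 0.95^13 = 48.7%; 1 − 0.95^26 = 73.7%

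**4. Simulation allowing for dependence.** The two tests on one endpoint are related, and so are the endpoints. Inputs from the documents: 120 patients allocated 40/40/20, that is 48/48/24 (sections 3 and 4), and about 70% women (section 4). Assumed, because the documents give no figure: equal correlation between endpoints of 0 to 0.5, and a responder rate of 25%. No group difference on any endpoint.

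| Set of tests | alpha 0.01 | alpha 0.05 (not stated in the plan) |
|---|---|---|
| Primary only, ANOVA and chi-square | about 1-2% | about 8-9% |
| 13 endpoints, both tests, whole sample | about 16-20% | about 52-66% |
| The same, plus the two sex strata | about 34-44% | not needed for the conclusion |

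Repeat runs agree to within about two points.

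**5. What the event is.** These figures count any significant omnibus result, including sham doing better or the two active arms differing. In 40,000 simulated null trials, 36% of ANOVA results significant at 0.01, and 39% at 0.05, also had an active arm significantly better than sham on an unadjusted pairwise test at the same level. If the chi-square tests behave alike and all 26 tests are independent:

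- alpha 0.01: 0.36 × 0.01 = 0.0036 per test; 1 − 0.9964^26 = about 9%
- alpha 0.05: 0.39 × 0.05 = 0.0195 per test; 1 − 0.9805^26 = about 40%

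**The case against.** The strongest reply is that the sentence in section 6.2 has a main clause, and it names a single primary endpoint. The text after it and Table 1 both keep the primary-secondary distinction. Nowhere do the documents say that one positive result among many makes the treatment a success, and section 6.2 also asks for a 30% change, so a p-value alone is not the criterion. If the claim rests on pain intensity, the risk is small even with two tests. The subgroup repeats are meant to show whether the effect depends on sex or diagnosis, which is a different question from overall efficacy.

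Much of this stands. A reader might infer that any single positive result counts as success, or that a false efficacy claim is more likely than not. The documents do not support either reading. The second needs an alpha of 0.05, which is never stated, or subgroup strata whose number is not given, and it treats every omnibus result as a claim of benefit over sham. Counted as active better than sham, the whole-sample figure stays below one half even at 0.05 (step 5), although a claim that one active technique beats the other would add to it.

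What does not stand is that naming a primary settles the matter. The plan never confines the claim to it, and it gives the secondaries efficacy standing in the same paragraph. Section 7 also uses the per-endpoint chi-square tests to identify the most efficacious technique, and the subgroup aim is to see whether each technique works better in particular diseases. Both are efficacy statements.

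**Conclusion.** The concern holds in a limited form. The plan has a primary endpoint but no rule tying the efficacy conclusion to it, no multiplicity control, and no deciding test or contrast for it. In the whole sample the chance of at least one significant omnibus result under no effect is about 16-20% at 0.01, at least three times a conventional 5%, and about 52-66% if section 7 is run at 0.05. With the two sex strata it is about 34-44% at 0.01. False claims of active better than sham are a subset of these.

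The figures rest on the assumed correlation and responder rate. Thirteen endpoints is a low count where a row has several instruments, and EEG and the six-month follow-up come on top. In the other direction, caregiver burden is available only for patients who have a caregiver. Neither changes the conclusion. The statement that a false claim is more likely than not should not be made from these documents.

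**What to change.** In section 6.2, replace the success-criteria wording with: Efficacy is concluded only from the primary endpoint, average daily pain intensity. Then, in section 7:

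- Name one deciding test for the primary, for example the group-by-time term of the repeated-measures ANOVA. State the two active-versus-sham contrasts, adjusted for two comparisons. Make the 30% responder rate supportive.
- State one two-sided alpha, consistent with the sample-size section.
- Report the secondary endpoints as supportive with Holm-adjusted p-values. Name one score per row so that the family is defined, and say how satisfaction, which has no baseline, is compared.
- Label subgroup, EEG and caregiver results exploratory. Moving caregiver burden out leaves 12 secondary endpoints in the Holm family, so the smallest p-value is judged against alpha/12 (0.01/12 = 0.0008, or 0.05/12 = 0.0042).

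This is a change of wording that needs no new data or patients. The cost is that some secondary results will lose nominal significance.
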